4.3.2 Relating immune response to clinical response

The relationships between immune and clinical responses will be assessed using a variety of statistical techniques. Preliminary explorations will be graphical in nature (e.g. boxplots, scatterplots). Univariate and multivariate modeling will be used quantify the associations. In the case of a binary clinical outcome (e.g. toxicity), logistic regression will be used. In the case of a time-to-event clinical outcome (e.g. OS), the Cox proportional hazards model will be used.

4.3.3 Longevity of an allogeneic vaccine

Pharmacokinetic studies will be used to evaluate the longevity of the allogeneic vaccine by measuring the levels of GM-CSF in the serum. Serum will be obtained from each research participant on days 0 and 3 of treatment. Pharmacokinetic parameters will be estimated, when possible, using standard compartmental models. Parameter estimates and normal theory standard errors will be calculated by fitting using weighted least squares. Summary statistics (e.g. mean, standard deviation) will be presented for each cohort on each day at each vaccine boost. Plots of the means against time will be included to assess the change in the parameters over time. The relationship between pharmacokinetic parameters and clinical outcomes will be assessed using logistic regression for binary outcomes (e.g. toxicity) and Cox proportional hazards models for time to event outcomes (e.g. OS, PFS).

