1.0 Study Synopsis

Objectives:

Primary:

1. To evaluate the safety of primary and boost vaccinations with lethally irradiated allogeneic pancreatic tumor cells transfected with the GM-CSF gene vaccine in the treatment of patients with surgically resected adenocarcinoma of the head, neck, or uncinate of the pancreas

Secondary:

1. To estimate the association of specific *in vivo* parameters of immune response including, but not limited to mesothelin, prostate stem cell antigen (PSCA), and mutated *k-ras*-specific T cell responses, with clinical responses in patients who are receiving semi-annual vaccine boosting with lethally irradiated allogeneic pancreatic tumor cells transfected with the GM-CSF gene.
2. To estimate the efficacy of vaccine boosts in the treatment of patients with adenocarcinoma of the pancreas in terms of overall and recurrence free survival.
3. To use the serum GM-CSF levels as a measure of longevity of an allogeneic vaccine following a semi-annual boosting with lethally irradiated allogeneic pancreatic tumor cells transfected with the GM-CSF gene.
4. To determine the psychosocial and symptom profiles of patients with pancreatic cancer treated with an irradiated allogeneic GM-CSF secreting vaccine, and to explore changes over time. The psychosocial profile will include information about, but is not limited to demographics, quality of life, hope, trust, social support, decision control and advanced directives. The symptom profile will include but is not limited to pain, anorexia, fatigue, and mood state.

Study population:

In order to be considered for this study, patients need to meet following major criteria for inclusion: History of surgically resected pathologic stage 1 (no direct tumor extension beyond pancreas and no regional lymph node metastases), 2 (direct extension of tumor beyond pancreas), and/or 3 (regional lymph node metastases) adenocarcinoma of the head, neck, tail, or uncinate of the pancreas.

Have no radiographic evidence of pancreatic cancer disease recurrence.

Have not received any anti-cancer therapy in the past 28 days.

Study Design:

Eligible subjects will receive by intradermal administration the pancreatic tumor vaccine consisting of two irradiated, allogeneic pancreatic tumor cell lines transfected with the granulocyte macrophage-colony stimulating factor (GM-CSF) gene. There will be two cohorts of research participants: those who have previously received the pancreatic cancer vaccine (up to 17) and those

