2.7.2 Serum GM-CSF Levels

Serum GM-CSF levels were measured in the patients participating in the first pancreatic tumor vaccine study at time 0, 24, 48, 72, 96 and 120 hours following the first vaccine. The peak concentration of serum GM-CSF levels was seen at 48 hours in 83% (5/6) of the patients who achieved a measurable serum GM-CSF level. Only one patient who received dose level one had a measurable serum GM-CSF level at a minimum level of 1.0 pg/ml at 48 hours. There was no measurable serum GM-CSF level in any of the six patients who received dose levels two and three at any time point. All five patients who received dose level four had measurable serum GM-CSF

levels with the range of 1.2 to 14.0 pg/ml. GM-CSF levels became undetectable by 120 hours in all patients on study. No side effects other than asymptomatic eosinophilia were associated with these low but detectable serum GM-CSF levels.

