4. Blood testing to include CBC/diff, absolute eosinophils, absolute neutrophils, absolute lymphocytes, comprehensive chemistry panel including electrolytes, albumin, BUN, creatinine, AST, ALT, total bilirubin, alkaline phosphatase, amylase, and CA 19-9.
5. Research blood: 20 cc for serum banking.
6. 10 cc for HLA typing and 10 cc for EBV testing for vaccine naïve research participants only.
7. Skin biopsy for vaccine naïve research participants only.
8. Pregnancy test for women of childbearing potential. Urine pregnancy test preferred.
9. Several psychosocial and symptom instruments, including: quality of life, hope, trust and pancreatic cancer survivor surveys. (See appendices for copies of the instruments).
10. If not previously enrolled on IRB # NA_00036444 (SKCCC J0248) entitled, Long term follow-up of patients who received lethally irradiated allogeneic pancreatic tumor cells transfected with the GM-CSF gene, the research participant will be encouraged to join the long-term follow-up study.

Day 0

1. Administration of vaccine (Topical lidocaine-based anesthetic may be placed 1-2 hours prior to planned vaccine administration time to the intended vaccine sites.)
2. Day 0 serum GM-CSF level
3. Vital signs before and after vaccine administration
4. Photograph of vaccine sites (if clinically indicated)
5. Assessment for toxicities
6. Monitor for 30 minutes after vaccine administration
7. Tetanus toxoid boost if last tetanus vaccination > 10 years. Tetanus/diphtheria (Td) may be substituted if tetanus alone is not available. If both are not available, no tetanus vaccine will be administered.
8. Provide diary to record vaccine reactions, health/medical complaints and medication changes.

Day 1

1. Vital signs
2. Assessment of vaccine sites. This will include: number of sites that have erythema, induration, pruritus, and tenderness; and measurement of induration and erythema of largest vaccine site.
3. Assessment for toxicities
4. Day 1 serum GM-CSF level
5. Photograph of vaccine sites (if clinically indicated)

Day 2

1. Day 2 serum GM-CSF level

Day 3

1. Vital signs
2. Assessment of vaccine sites. This will include: number of sites that have erythema, induration, pruritus, and tenderness; and measurement of induration and erythema of largest vaccine site.
3. Assessment of toxicities

4. Day 3 serum GM-CSF level
5. Heme-8 with differential, including absolute eosinophil count, absolute neutrophils, absolute lymphocytes

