3.4.3 Evaluation for Safety and Anticipated Toxicities

Severe toxicities are unlikely, based on information from previous GM-CSF gene vaccine studies completed here at Johns Hopkins Hospital trials, including the Phase I and II pancreatic tumor vaccine trials. In experiments involving over 400 mice, use of irradiated GM-CSF secreting tumor cells caused only reversible lymphadenopathy and reversible subcutaneous swelling; no ulcerations were seen. In our first phase I trial in patients with renal cell carcinoma, only local erythema and swelling were seen following intradermal injections of cell doses up to 4×10^7 GM-CSF modified vaccine cells, and up to 4×10^8 unmodified vaccine cells.

At the highest dose level, we predict that initially 45 mcg of total GM-CSF will be secreted locally per 24 hours, a level that will diminish as tumor cells are killed by invading inflammatory cells. To support hematologic recovery in oncology patients after intensive chemotherapy, subcutaneous or intravenous doses of GM-CSF between 5 and 10 ug/kg/day are commonly used (350-700 mcg total for a 70 kg individual). At this dose range the following side effects are commonly seen: local or generalized skin rashes, bone pain (attributed to stimulation of hematopoietic progenitors), fever, and malaise. Although patients in the initial Phase I study of the allogeneic tumor vaccine had normal bone marrow function, leukocytosis and toxic levels of serum GM-CSF did not occur with the 10 fold lower dose of GM-CSF. The maximum serum GM-CSF level obtained was 14.0 pg/ml with dose level four at 48 hours after the first pancreatic tumor vaccine.

The plasmid used to transfect the GM-CSF gene is safe. In contrast to retroviral vectors, it lacks the coding sequences that would allow replication and the generation of helper virus. This plasmid containing the GM-CSF gene has been sequenced following vector construction to confirm its insertion, orientation, and the lack of mutations. In addition, this vector has been confirmed to produce bioactive GM-CSF.

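### Section 4.3.3 rests vaccine longevity on compartmental fits made only when possible; low GM-CSF levels and at most four post-vaccine samples leave these poorly identified, and patients with low or brief levels may have none

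*Combined protocol and SAP*

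**What the plan says.** Secondary objective 3 in section 1.0 is "To use the serum GM-CSF levels as a measure of longevity of an allogeneic vaccine following a semi-annual boosting". Section 4.3.3 is the whole of the corresponding analysis. It states "Pharmacokinetic parameters will be estimated, when possible, using standard compartmental models" and then "Parameter estimates and normal theory standard errors will be calculated by fitting using weighted least squares". It promises means and standard deviations by cohort, day and boost, and relates the parameters to toxicity by logistic regression and to OS and PFS by Cox models. It does not say when a fit counts as possible, what quantity represents longevity, how undetectable values are handled, or what happens to patients without a fit.

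On sampling, section 4.3.3 says "Serum will be obtained from each research participant on days 0 and 3 of treatment". Section 3.4.1.1 instead lists samples on each of days 0 to 4 of Vaccination #1 (for example "Day 1 serum GM-CSF level"). That vaccination is the first boost for the previously vaccinated cohort. The schedule for later boosts in section 3.4.1.4 lists no GM-CSF sample, and neither does Table 3 as it can be read.

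On the expected data, section 3.4.3 describes local secretion as "a level that will diminish as tumor cells are killed by invading inflammatory cells". Section 2.7.2 reports that all five phase I patients at dose level four, the dose used here, had measurable "levels with the range of 1.2 to 14.0 pg/ml". The lowest value reported at any dose is 1.0 pg/ml, and all patients were undetectable by 120 hours.

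**The concern.** A standard compartmental model describes what happens to a known input. Here the input is secretion by cells that are being killed, so it is unknown, differs between patients and falls over time. Its duration is the very thing the objective asks about, yet it is not a standard output of such a model.

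With levels this close to the lowest reported value, some patients may have too few quantifiable samples to fit. Whether a patient can be fitted then depends on how high and how long GM-CSF was detectable, which is the quantity being measured. If only fitted patients contribute, the summaries describe a selected group, and the toxicity, OS and PFS models lose the low-exposure end.

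**Working it through.** **1. The plan's own figure.** The longevity analysis has no sample-size or precision figure. The one GM-CSF proportion, in section 2.7.2, reproduces: patients with a measurable level number 1 (dose level one) + 0 (levels two and three) + 5 (level four) = 6, and 5/6 = 83% peaked at 48 h. It is itself conditional on having a measurable level.

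**2. Identifiability.** Take one compartment with volume V, elimination rate k and secretion S0·exp(-λt). Then

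C(t) = (S0/V)/(k - λ) × [exp(-λt) - exp(-kt)].

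- Only the ratio S0/V appears, so volume and clearance cannot be separated from the unknown secretion rate.
- Exchanging k and λ leaves the curve unchanged. Even perfect data cannot tell whether the late decline reflects loss of cells or elimination of GM-CSF.

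**3. Parameters against samples.** The curve has three free quantities (S0/V, λ, k). Taking day 0 as baseline:

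- Days 0 and 3 give one post-vaccine value, so nobody can be fitted.
- Days 0 to 4 give four values, leaving 4 - 3 = 1 residual degree of freedom if all four are quantifiable.

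**4. Measurability at this dose.** In phase I it was 5/5. The exact 95% lower limit is 0.025^(1/5) = 47.8%, so up to 52% non-measurable is compatible with the data (45 × 0.522 = about 23 of 45 vaccine-naïve patients).

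**5. Illustration with fixed profiles.** Assumptions: limit 1.0 pg/ml; peak P at 48 h, log-uniform on 1.2 to 14; 24 h level 0.5P; later levels P·2^(-24/h) at 72 h and P·2^(-48/h) at 96 h. The longest half-life that takes 14 down to 1.0 between 48 and 120 h is h = 72/log2(14) = 18.9 h. At h = 15 h, for example, the 72 h level is quantifiable if P ≥ 2^1.6 = 3.03, so the share with two or fewer points is ln(3.03/1.2)/ln(14/1.2) = 38%.

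| Half-life | Two or fewer points | Fewer than four points | Mean last detectable, all | Mean last detectable, three or more points |
|---|---|---|---|---|
| 12 h, shared | 49% | 100% | 60 h | 72 h |
| 15 h, shared | 38% | 83% | 67 h | 79 h |
| 18.9 h, shared | 28% | 64% | 74 h | 84 h |
| 72/log2(P), per patient | 0% | 21% | 96 h | 96 h |

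The last row gives each patient the longest half-life that still reaches 1.0 at 120 h. The 72 h and 96 h levels are then P^(2/3) and P^(1/3), always above 1.0. Only the 24 h value can be lost, when P < 2: ln(2/1.2)/ln(14/1.2) = 21%. In this row selection does not change mean last detectable time at all.

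**6. Illustration with varying half-lives.** Assumptions: lognormal peak (log-SD 0.7), median half-life 1 day (log-SD 0.4), correlation of peak with half-life from -0.5 to 0.5, limit 1.0, samples on days 1 to 4, and a fit that needs at least three quantifiable samples. Ratios compare fitted patients with all patients.

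| Median peak (pg/ml) | Fitted | Time above limit, ratio | Half-life, ratio |
|---|---|---|---|
| 2 | 58–59% | 1.39–1.47 | 0.95–1.18 |
| 4 | 83–91% | 1.07–1.13 | 0.98–1.07 |
| 8 | 96–99% | 1.01–1.03 | 1.00–1.02 |

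If the fit also needs two samples after the observed peak, the ratios span 1.00–1.44 for time above the limit and 0.93–1.15 for half-life.

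**The case against.** - **Overstated longevity as a fact.** A reader might infer that the plan will overstate longevity, with some 28–49% of patients lost. The documents do not support that. The range comes from the shared-half-life rows, and 18.9 h is a ceiling only for a patient who peaks at 14; one peaking at 4 could have 72/log2(4) = 36 h. Section 2.7.2 does not say that 1.2 was anyone's peak, and no assay limit is stated. When all patients share one half-life, dropping some cannot change its mean, and when half-lives vary the bias has no fixed sign. This objection stands in full.
- **All five patients at this dose were measurable.** True, and the loss may be small. But measurable at one time is not the same as fittable, and five patients leave wide uncertainty.
- **The input is not wholly unknown.** Section 3.4.3 predicts 45 mcg per 24 h initially, which matches 90 ng per 10^6 cells × 500 = 45 mcg. That is one initial rate from culture, the same for everyone, with no rate of decline. It does not supply the patient's input.
- **Daily summaries need no fit.** If the planned means by day are of GM-CSF levels, they escape the problem. The text does not say whether they are of levels or parameters, and it has no rule for undetectable values. The outcome models use the parameters explicitly.
- **No exclusion rule is written.** Correct. Loss of unfitted patients from the regressions is the default when a covariate is missing, not a stated intention.
- **Days 0 and 3 alone would leave nobody fitted.** On that reading there is no selective loss because there is no analysis. The contradiction must be resolved first, and resolving it in favour of days 0 to 4 does not remove the present problem.
- **Section 4.3 calls these endpoints descriptive.** It does, which limits the consequence.

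**Conclusion.** The point holds as one about method and selection. Volume and clearance are not identifiable from these data. The remaining parameters rest on at most one residual degree of freedom, and fitting only when possible selects patients on the quantity being measured.

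Restriction to fitted patients would tend to overstate time detectable. The amount cannot be fixed from the documents: the illustrations run from no inflation to 47%, depending on assumed peaks, half-lives, assay limit and fit criterion. A fitted half-life could be biased in either direction (-7% to +18% in the same illustrations). All these sizes are conditional on an assumed limit of 1.0 pg/ml and on days 0 to 4 being sampled.

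A claim that the problem is worst at later boosts would also go too far, because no GM-CSF sample is listed there. The sample size, the stopping rule and the primary safety analysis are unaffected. The change is worth making because secondary objective 3 has no other defined analysis.

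**What to change.** 1. Reconcile the sampling days in section 4.3.3 (days 0 and 3) with section 3.4.1.1 (days 0 to 4), and state which boosts have GM-CSF samples. As written, only the first vaccination does, so objective 3 is covered for the previously vaccinated cohort's first boost and not for later ones.
2. State the assay limit. Treat a missed sample as missing, not as undetectable.
3. For every sampled patient, make these the main measures:
   - time to undetectable, interval-censored between the last detectable and first subsequent undetectable sample, right-censored if still detectable on day 4, with never-detectable patients kept in (for instance left-censored at the first post-vaccine sample);
   - observed maximum level;
   - AUC over 0 to 96 h, with undetectable values treated as left-censored and never dropped.
4. Use these measures in the logistic and Cox models for all sampled patients. As a covariate, time to undetectable can enter as the last detectable sampling day.
5. Report percent detectable and median level by day and cohort.
6. Keep any compartmental fits as supportive, with a stated fit criterion and the numbers fitted and not fitted.

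For Vaccination #1 this costs only SAP wording and a simpler analysis of samples already scheduled on days 0 to 4. Covering later boosts would need added samples. The small loss is that clearance and volume are no longer main results.

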4.3.4 Psychosocial and symptom profiles

The psychosocial and symptom profiles will be evaluated through the use of a variety of surveys and measurement tools. Surveys will be administered at several time points: day 0 and day 28 of the each vaccination. The responses will be measured using 8 techniques described in Section 5.3 and include topics such as concept of hope, symptom burden, patient satisfaction, and QOL. Categorical measurements such as those based upon Likert scales (e.g. Hearth Hope Index) will be summarized using counts, medians, ranges and estimates of the probability distributions. Continuous variables will be summarized using means and standard deviations. Trends over time

will be summarized by plotting the median measurements against time with an estimate of variability (e.g. standard deviation, inter-quartile range) for each cohort. Associations between measurements will be evaluated graphically (e.g. boxplots, scatterplots) and numerically (e.g. Spearman's correlation). Comparisons between time points will be made using non-parametric techniques (e.g. Kruskal-Wallis test, χ^2 test).

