Research participants must meet the following criteria.

1. Received the last lethally irradiated GM-CSF transfected allogeneic pancreatic cell lines Panc 10.05 and Panc 6.03 at least 12 months prior (+/- 30 days).
2. Have an Eastern Cooperative Oncology Group (ECOG) performance status of 0 or 1.
3. Have adequate hematologic function (Hemoglobin \geq 9 gm/dl, ANC \geq 1500,/cu mm, platelets \geq 100,000/cu mm)
4. Have adequate renal function (Serum creatinine \leq 2 mg/dl).
5. Have adequate hepatic function (Bilirubin \leq 2.0 mg/dl, unless known Gilbert's Syndrome; AST, ALT and amylase \leq 2x upper limit of normal: Alk Phos \leq 5x upper limit of normal.)
6. Agree to use adequate birth control, if of childbearing potential.

[figure not shown]
[figure not shown]
3.2.5 Exclusion Criteria for Boost Vaccination:

[figure not shown]
Patients with any of the following will be excluded from study entry or will not be able to continue:

1. Radiographical evidence of pancreatic cancer disease recurrence.
2. Documented history of autoimmune diseases including systemic lupus erythematosus, sarcoidosis, rheumatoid arthritis, glomerulonephritis, or vasculitis.
3. Uncontrolled medical problems.
4. Systemic steroid therapy within 28 days before vaccine administration (except for short-term steroid therapy ending at least two days prior to vaccine administration).
5. Anticipated need for systemic steroid therapy within 28 days after vaccine administration.
6. Evidence of active infections.
7. Pregnant.

[figure not shown]

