3.4.6 Off-study

Research participants will be discontinued from participating in this study for the following circumstances:

- ◆ There is radiographic evidence of pancreatic cancer recurrence.
- ◆ Serious vaccine related adverse events occur.
- ◆ The vaccine supply is exhausted.
- ◆ The research participant is noncompliant, is unable to comply with the treatment plan, or requests withdrawal.
- ◆ The research participant is receiving concomitant immunotherapy, chemotherapy, radiotherapy, or other biological or gene therapy.

If determined to be off-study, the research participant will be followed for 28 days after the administration of the last vaccine for toxicities related to the vaccine, or longer, if vaccine-related toxicities occur. Whenever possible, the research participant will be asked to have the tests indicated for the day 28 visit as the off-study visit, unless this was done within 28 days of the off-study date.

If the research participant consents there will be a lifelong follow-up through participation in [name] study, IRB # NA_00036444 (SKCCC J0248) entitled, Long term follow-up of patients who received lethally irradiated allogeneic pancreatic tumor cells transfected with the GM-CSF gene.

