Measurements of immune response include but are not limited to mesothelin, prostate stem cell antigen (PSCA) and mutated k-ras-specific T cell responses. Continuous variables will be summarized with means and standard deviations. Dichotomous and categorical variables will be

summarized using proportions with exact 95% confidence intervals and counts, respectively. These summaries will be computed for each patient at two time points around each vaccine boost: pre-vaccination and four weeks post vaccination. Plot will be used to show the changes in immune response over time both for each individual and for each cohort. For each vaccine boost, comparisons in the pre and post-vaccine responses will be compared using paired t-tests (or Wilcoxon signed rank tests if appropriate) for continuous variables and Fisher's exact test for dichotomous or categorical variables. Associations between immune responses will be explored graphically (e.g. scatterplots, boxplots) and numerically (e.g. correlations, χ^2 tests).

Measurements of antitumor immunity include but are not limited to the measurement of shared tumor-specific antigens and k-ras specific antitumor immune responses. Autologous lymphocytes will be obtained from peripheral blood before each vaccination, and at four weeks following each vaccinations. The graphical and numerical analyses of these results will be the same as that described for measurements of immune responses and will be carried out for each cohort separately.

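### Section 4.3.4 tracks quality of life with cohort medians and unpaired tests, so its trend plot can mix change in patients with change in who is still surveyed

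*Combined protocol and SAP*

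**What the plan says.** The fourth secondary objective (Study Synopsis) is to describe psychosocial and symptom profiles "and to explore changes over time".

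Section 4.3.4 sets the timing: "Surveys will be administered at several time points: day 0 and day 28 of the each vaccination". Trends "will be summarized by plotting the median measurements against time with an estimate of variability", separately for each cohort, with the standard deviation or inter-quartile range as examples of the variability measure. It adds: "Comparisons between time points will be made using non-parametric techniques", with Kruskal-Wallis and chi-square as the examples. It gives no change score, pairing, rule for missing surveys, defined set of patients or count of patients behind each point.

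Other sections decide who reaches a later time point:
- Section 3.4.6 lists as a reason for leaving the study: "There is radiographic evidence of pancreatic cancer recurrence".
- Section 3.2.5 excludes from any boost: "Radiographical evidence of pancreatic cancer disease recurrence".
- Section 3.2.4 lists as a condition for each boost: "Have an Eastern Cooperative Oncology Group (ECOG) performance status of 0 or 1".

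For immune data, Section 4.3.1 plans more: "Plot will be used to show the changes in immune response over time both for each individual and for each cohort". It also plans paired t-tests or signed-rank tests of continuous measures before and after each boost.

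**The concern.** A median taken at each time point, and a test that treats time points as independent groups, describe a series of groups. They do not describe change in patients. If surveys continue at boosts, a patient with recurrence drops out of all later points, and a patient with ECOG above 1 drops out for as long as that lasts. If those who leave tend to have lower quality of life or hope, or more symptoms, the median of those remaining drifts towards better values although nobody has changed. Keeping the two cohorts apart does not prevent this, because the selection acts within each cohort.

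The stake is interpretation. Such a curve could be read as improvement during vaccination and carried into hypotheses for later trials. Conversely, unpaired tests discard the within-patient correlation and so can miss a real change.

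**Working it through.** The plan gives no sample size, effect or dropout figure for this endpoint, so there is no stated figure to reproduce.

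**1. When surveys are taken**

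| Place | Surveys? |
|---|---|
| 4.3.4 | Day 0 and day 28 of every vaccination |
| 5.3 | Days 0 and 28 |
| 3.4.1.1 to 3.4.1.3, itemised lists | Vaccination #1, primes #2 and #3, day 28 after prime #3 |
| 3.4.1.4, text on delayed boosts and on the day-28 boost visit | Mentioned |
| 3.4.1.4, itemised boost lists | None |
| Table 3 (prime #1 and each boost) | None |
| Off-study visit | Mailing is mentioned, but no survey is in the itemised list |

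Table 3 is weak evidence either way. It also omits surveys for prime #1, where Section 3.4.1.1 lists them. Both schedules are therefore carried forward.

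**2. Proportion leaving (vaccine-naïve cohort, illustrative)**

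Section 2.7.3 gives 6/14 = 0.43 disease free at one year in the phase I study. I assume a constant hazard and apply it from first vaccination.
- First boost: primes fall on days 0, 28 and 56, and the boost six months after the third. 56 days is about 1.8 months, so the time is 1.8 + 6 = 7.8 months. Leaving: 1 − 0.43^(7.8/12) = 1 − 0.578 ≈ 0.42.
- Priming only: the last itemised survey is at 3 × 28 = 84 days. Leaving: 1 − 0.43^(84/365) = 1 − 0.823 ≈ 0.18.

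**3. Shift in the mean with no individual change**

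Let p be the proportion leaving, S the baseline mean of stayers and L that of leavers. The overall mean is (1 − p)S + pL, so the mean of those remaining exceeds it by p(S − L). I assume S − L = 5 to 15 points on a 0–100 score.
- Surveys up to a first boost: 0.42 × 5 = 2.1; 0.42 × 15 = 6.3.
- Surveys in priming only: 0.18 × 5 = 0.9; 0.18 × 15 = 2.7.

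**4. The planned statistic, the median**

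In a simulation (4,000 runs per setting) each patient keeps one fixed score (assumed mean 65, SD 20). Time to leaving has a latent correlation with that score. At 43% retention:

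| Correlation | Rise in median, n = 17 / n = 45 | Chance that the later median exceeds baseline, n = 17 / n = 45 |
|---|---|---|
| 0 | −0.1 / −0.1 | 46% / 46% |
| 0.2 | 3.6 / 3.6 | 66% / 78% |
| 0.3 | 5.6 / 5.4 | 77% / 89% |
| 0.5 | 9.0 / 9.1 | 91% / 99% |

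True change is zero throughout, and within-patient change from baseline is exactly zero in every row.

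**5. The tests**

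In the same runs, Kruskal-Wallis across five time points (retention 100, 75, 60, 43 and 30%) rejected in at most 1.2% of runs for correlations up to 0.3, and in up to 16% at 0.5 with n = 45. The false trend is therefore mainly in the plot.

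For a true 5-point shift between two time points (SD 20, 3,000 runs), power was:

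| n | Within-patient correlation | Kruskal-Wallis | Signed-rank |
|---|---|---|---|
| 45 | 0.7 | 9% | 54% |
| 45 | 0.5 | 13% | 37% |
| 17 | 0.7 | 2% | 21% |
| 17 | 0.5 | 4% | 15% |

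**The case against.** - **The plan does not say that all available patients are used.** This is so: no analysis set is stated, and the two tests are only examples, so a paired test is not ruled out. But both examples are unpaired, and a median at each time point with no stated set is most naturally taken over those who answered.
- **Selection on health is not shown.** A reader might infer that every later point must hold a healthier group. The documents do not support that. Recurrence is radiographic, and patients also leave by withdrawal, noncompliance or exhausted vaccine supply. Everyone enters recurrence-free, with ECOG 0 or 1 and at least 28 days off anti-cancer therapy. Nothing links survey scores to leaving, and with no correlation there is no drift. This stands, and makes the point conditional.
- **Boost surveys may not exist.** If the itemised lists govern, attrition over 84 days is modest, and the previously vaccinated cohort has one itemised survey point and no trend. This stands until the sections are reconciled.
- **The attrition figure is borrowed.** It comes from 14 phase I patients timed from diagnosis, not from first vaccination. It should not be applied to the previously vaccinated cohort, who according to Section 4.1 are recurrence-free for at least a year after treatment. This stands.
- **Exit scores are partly provided for.** Surveys may be mailed around the off-study visit, but the itemised list there has none and Section 4.3.4 makes no use of them.
- **A median among those still on study is legitimate.** As a description of longer-term survivors, the interest stated in Section 5.3, it is. It does not answer the objective of exploring change.
- **The analyses are descriptive** (Section 4.3). True, and this limits the harm.

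**Conclusion.** The point holds in conditional form and is minor. As written, Section 4.3.4 cannot separate change within patients from change in who remains, and its named tests ignore pairing. The plotted median can improve with no change in any patient if lower scores go with earlier departure. The effect is material only if surveys are taken at boosts.

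Under the assumed 5 to 15 point gap and borrowed hazard, the mean shifts about 2 to 6 points by a first boost, or about 1 to 3 points if surveys stop after priming. These figures are illustrations for the vaccine-naïve cohort only. The documents give neither the score distribution nor any link between scores and leaving.

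A reader might go further and conclude that the trial will report a spurious improvement, or that the tests will declare one. Neither follows. The first needs a correlation that no section supplies, and the simulated tests seldom rejected falsely unless that correlation was strong. The primary safety result is untouched.

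**What to change.** - Make within-patient change from Day 0 of vaccination #1 the summary at each time point, with the number of patients contributing.
- Replace Kruskal-Wallis and chi-square for comparisons between time points with paired tests, such as Wilcoxon signed-rank for scores and McNemar for binary items. Section 4.3.1 already plans paired tests for continuous immune measures.
- Draw the trend plot by last time point on study, or in a fixed set of patients with all surveys up to that time.
- Reconcile Sections 4.3.4 and 5.3 with the itemised boost lists in Section 3.4.1.4 and with Table 3, so that the survey time points are unambiguous.

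A mixed model is optional and not needed here. With at most 45 and 17 patients, partly ordinal scales and dropout that includes death, it brings assumptions of its own.

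The cost is plan wording and modest analysis of data already collected. The downside is small: later summaries rest on fewer patients, and within-patient change does not recover the scores of those who left.
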